8.4 Statistical Methods

All analyses, summaries, and listings will be performed using SAS[®] software (Version 9.2 or higher).

Baseline characteristics, efficacy and safety data will be summarized using the appropriate descriptive statistics.

For the efficacy variables, descriptive statistics (including n, SD, mean, minimum, maximum, and 95% CI) for the changes from Baseline during the 6-week treatment period will be presented.

Continuous variables will be summarized by descriptive statistics (sample size [n], mean, SD, median, minimum, and maximum). Categorical variables will be summarized in frequency tables (n, frequencies, and percentages). Individual subject data will be presented in listings.

All statistical tests of treatment effects will be performed at a 2-sided significance level of 0.05, unless otherwise stated.

Additional details concerning statistical methods are presented in the SAP.

All references to study medication refer only to the double-blind treatment period.

8.4.1 Analysis Populations

Four analysis sets will be used in analyzing the data obtained from this protocol:

Intent-to-Treat (ITT): includes all consented and randomized subjects. Regardless of any protocol deviations, analyses performed on the ITT set will be based on the randomized treatment assignment and all available data.

Full Analysis Set (FAS): includes all consented and randomized subjects who have had at least 1 patch of double-blind study medication applied and who have a Baseline PANSS total score and at least 1 post-Baseline assessment of the primary efficacy measure (PANSS total score). Evaluable subjects will be defined as those who meet the FAS definition. The FAS will be used as the primary set for analysis of efficacy endpoints based on randomized treatment assignment.

Safety Analysis Set (SAF): includes all subjects who have had at least 1 patch of double-blind study medication applied and who have at least 1 post-dose safety measurement during the double-blind treatment period. In the unlikely event that errors may have occurred in treatment arm assignments, then analyses using the SAF will be based on treatment actually received. The SAF will be used for the analysis of dermal evaluations and safety endpoints.

Pharmacokinetic Analysis Set (PAS): includes all subjects who have received at least 1 dose of study medication during the double blind treatment period and have at least 1 blood sample for PK assessment. Subjects may be excluded from the PAS set if they significantly violate inclusion or exclusion criteria, significantly violate the protocol in a way that may

Noven Pharmaceuticals, Inc.
HP-3070-GL-04
HP-3070

71

influence the PK analysis, if any unexpected error occurs during the study that may influence the PK analysis (e.g., early detachment of transdermal systems, apparent sample switching, etc.) or if their data are unavailable or incomplete. The PAS will be used for the analysis with model based approach. Excluded cases will be documented together with the reason for exclusion.

8.4.2 Primary Efficacy Analysis

The primary efficacy analysis (the analysis of the primary variable) will be performed on the Full Analysis Set (FAS).

The primary efficacy variable, change from Baseline to Week 6 in the PANSS total score for each of the 3 treatment arms, will be analyzed using a mixed model repeated measures (MMRM) analysis. The MMRM model will include change from Baseline in PANSS total score as the repeated dependent variable, with country, treatment (HP-3070-9.0 [9.0 mg], HP-3070-18.0 [18.0 mg], and placebo), visit, treatment by visit interaction, and the Baseline PANSS total score as covariates. An unstructured covariance matrix will be assumed. In the event the convergence cannot be attained with the unstructured correlation matrix, the following alternative structures will be attempted in the specified order (from least to most restrictive): heterogeneous Toeplitz structure (TOEPH), heterogeneous autoregressive (1) (ARH[1]), heterogeneous compound symmetry (CSH), No Diagonal Factor Analytic (FA0[q], with q equal to the number of time points), Toeplitz structure (TOEP), autoregressive (1) (AR[1]), and compound symmetry (CS). If either ARH(1) or AR(1) structure is used, a random subject intercept will also be included in the model.

The MMRM model may be repeated on additional analysis sets as a sensitivity analysis.

If the normality assumption is violated, ANCOVA analysis on rank-transformed data will be used as a supportive analysis.

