5.5 Method of Assigning Subjects to Treatment

Subjects will be randomly assigned to treatment using a 1:1:1 ratio to 1 of 3 treatment arms (HP-3070-9.0, HP-3070-18.0, or placebo) stratified by country.

Once the subject meets all the eligibility criteria for randomization in the double-blind Treatment Period, the study center will request the study medication assignment using the Interactive Voice Activated Response System (IVRS) or Interactive Web-based Response System (IWRS). All randomized subjects will be managed by IVRS/IWRS. Detailed information will be provided in the Study Manual.

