8.0 STATISTICAL METHODS

8.1 Determination of Sample Size

Assuming an effect size of 0.35 on the change in PANSS total score from baseline to Week 6 for the 2 pairwise comparisons between each active HP-3070 treatment arm and placebo, the power for detecting a statistically significant HP-3070 advantage will be approximately 0.90 having 204 evaluable subjects per each treatment arm using a 2-side alpha level of 0.025 for each comparison. A 2-sided overall Type I error is equal to 0.05. Having 3 treatment arms, the total number of subjects randomized in the trial and included in primary analysis set will be approximately 612. A sufficient number of subjects will be screened to randomize the proposed sample size.

The effect size of 0.35 was chosen based on the lowest effect size observed in results from the studies conducted with SL asenapine and approved by FDA (Sycrest[®]/SAPHRIS[®] [Study 041004, and Study 041023]).

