8.2.1 Procedures for Sample Size Recalculation

The expected common (pooled) standard deviation is 20, which corresponds to a difference in means of 7 for our assumed effect size of 0.35. Using the transferred blinded data, the independent statistician will calculate the following metrics for the primary endpoint (PANSS Total Score):

- The common (pooled) SD

Using these metrics and the original assumptions of mean difference in reduction of PANSS scores from Baseline to Week 6, between treatment arms Type I error rate (0.025) and 90% power of the new sample size will be recalculated. More details, including decision rules and maximum increase in sample size, are available in the Statistical Analysis Plan (SAP). The independent statistician will provide a report which will include the following:

- Re-estimation of sample size
- The common SD for the primary endpoint

Noven Pharmaceuticals, Inc.
HP-3070-GL-04
HP-3070

69

Based on the documented SSR and the observed dropout rate, the independent statistician may recommend a new sample size to be sent to the Sponsor for final decision.

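### The primary MMRM holds the baseline-PANSS slope equal across all six visits; a baseline-by-visit term would protect the precision of the Week 6 contrast at practically no cost

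*Protocol*

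**What the plan says.** Protocol 8.4.2 makes the primary analysis an MMRM on change from baseline in PANSS total score, in the FAS, with an unstructured covariance matrix. Its fixed effects are country, treatment, "visit, treatment by visit interaction, and the Baseline PANSS total score as covariates". The synopsis gives the same list. Section 8.4.3 uses the same model for the key secondary endpoint, CGI-S, and 8.4.4 uses it for the other continuous secondary endpoints.

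The PANSS row of Table 1 has eight marks, which I read as Screening, Baseline and Weeks 1 to 6, so there are six post-baseline visits. The contrast that matters is at Week 6 (8.3.1).

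The sample size rests on these statements:

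- "Assuming an effect size of 0.35 on the change in PANSS total score from baseline to Week 6" (8.1)
- power that "will be approximately 0.90 having 204 evaluable subjects per each treatment arm", "using a 2-side alpha level of 0.025 for each comparison" (8.1)
- "The expected common (pooled) standard deviation is 20, which corresponds to a difference in means of 7 for our assumed effect size of 0.35" (8.2.1)

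Neither the sample-size section nor the recalculation section mentions any gain from baseline adjustment.

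**The concern.** With treatment-by-visit in the model and baseline only as a main effect, the slope used to adjust the Week 6 contrast is not the Week 6 slope. It is a generalised-least-squares average over six visits. Change scores usually vary less at early visits, so under an unstructured covariance those visits carry most of the weight.

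Change from baseline is zero at Day 0 by construction and is expected to grow over six weeks. If improvement is roughly proportional to initial severity, which is how the protocol's 30% responder definition expresses it, the slope steepens as improvement grows. The slope applied at Week 6 would then be too shallow.

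At stake are precision at the one visit that defines the primary endpoint, and the correction of whatever chance baseline imbalance the trial happens to have. The model has to be fixed before unblinding, so the choice cannot wait until the data show how the slope behaves.

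**Working it through.** **1. The protocol's own figure.** The inputs are difference 7, SD 20 and two-sided alpha 0.025 per comparison, so z = 2.2414; for 90% power z = 1.2816.

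- n per arm = 2 × (2.2414 + 1.2816)² × 20² / 7² = 202.6, rounded up to 203. The protocol has 204.
- Power at 204: the standard error is 20 × √(2/204) = 1.980, and 7/1.980 - 2.2414 = 1.293, which gives 0.902.

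The stated 0.90 is reproduced with no credit for baseline adjustment.

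**2. Assumptions.** The protocol gives no baseline SD, visit-specific slopes, correlations or dropout rate. I assumed:

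- baseline SD of 8, 10 or 12;
- SD of change rising from 10 at Week 1 to 20 at Week 6;
- residual correlation either autoregressive at 0.85 or exchangeable at 0.6;
- slopes b₁ to b₆ moving in equal steps between the end points shown in the table.

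**3. Formulas.** S is the residual covariance over the six visits.

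- Common slope: b_c = (1′S⁻¹b) / (1′S⁻¹1).
- Week 6 variance with the interaction: σ₆² = 20² - b₆² × var(baseline).
- Week 6 variance with the common slope: σ₆² + (b₆ - b_c)² × var(baseline).
- Part of a 1-point baseline difference left uncorrected: |b₆ - b_c|.

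**4. One case in full.** Slopes -0.10 to -0.50, baseline SD 10, autoregressive correlation.

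- b_c = -0.107, almost exactly the Week 1 slope.
- With the interaction: 400 - 0.25 × 100 = 375, so SD 19.36.
- With the common slope: 375 + (0.393)² × 100 = 390.4, so SD 19.76.
- The variance ratio is 1.041, and power is 0.909 against 0.921.
- One SD of chance imbalance in the arm means is 10 × √(2/204) = 0.99 point, and it shifts the estimate by 0.39 point.

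With exchangeable correlation the common slope is -0.053, shallower than the slope at any visit, and the variance ratio is 1.053.

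**5. Range over baseline SD 8 to 12 and both correlation patterns, complete data, 204 per arm.**

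| Slope, Week 1 to Week 6 | Extra Week 6 variance | Power, common slope | Power, by visit |
|---|---|---|---|
| -0.30 throughout | 0 | 0.906–0.912 | 0.906–0.912 |
| -0.05 to -0.30 | 1.0–2.9% | 0.903–0.905 | 0.906–0.912 |
| -0.10 to -0.50 | 2.6–7.9% | 0.905–0.913 | 0.914–0.928 |
| 0 to -0.50 | 4.0–12.2% | 0.896–0.903 | 0.914–0.928 |

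Across the three steepening rows, a 1-point baseline difference is left uncorrected by 0.25 to 0.56 point. A separate check of the -0.10 to -0.50 case gave a common slope of about -0.06 to -0.12 and 2.5–7.5% extra variance. A path of 0 to -0.80 would give 11–35%, but I regard it as extreme and do not rely on it.

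**6. Simulated MMRM, 204 per arm, 400 to 700 trials per setting.** Common slope is given first, by-visit second.

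- Slopes -0.10 to -0.50, complete data: mean estimates -7.02 and -7.02, power 0.900 and 0.910.
- The same slopes with about 30% dropout missing at random: means -6.97 and -6.96, power 0.827 and 0.842. The fall from 0.90 is due to dropout and occurs in both models.
- Type I error per comparison: 0.023 and 0.027 against a nominal 0.025, within simulation error.
- Constant slopes: mean standard error 1.959 in both models, and 2.190 in both with dropout. The extra parameters cost nothing visible.

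The Monte Carlo error of a power near 0.90 is √(0.09/400) = 0.015 at 400 trials, so the simulated power differences fit step 5 but do not measure it precisely.

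**The case against.** The strongest reply is that nothing here is wrong. A baseline main effect with treatment-by-visit and an unstructured covariance is a valid, prespecified model, and the synopsis, 8.4.2 and 8.4.3 agree with one another. The trial was sized on SD 20, so what is lost is a bonus the design never counted on. All of that stands, and it is why this is an improvement and not an error. Section 8.4 also leaves further statistical detail to the SAP, which is not at hand. But 8.4.2 and the synopsis spell out the model terms, so the protocol text is where the term is missing.

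Three stronger readings are tempting, and the documents do not support them.

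- **A reader might infer that the Week 6 contrast is under-adjusted as a matter of fact.** That holds only if the slope changes over visits. The protocol neither shows nor denies this, and with constant slopes the loss is zero.
- **A reader might infer bias, or that the missing-at-random basis of the MMRM fails.** Missing at random describes the dropout mechanism, and an omitted interaction does not alter it. What the omission can do is misspecify the mean model. A large run (150,000 per arm, 23% placebo and 13% active dropout, true effect -7) gave -7.13, -7.08 and -7.10 with the common slope, and -7.09, -6.98 and -6.96 by visit. The Monte Carlo standard error is at least 20 × √(2/150,000) = 0.073, so misses of 0.08 to 0.13 are within two standard errors. The gaps between the two fits are 0.04 to 0.14 point, at most 2% of the effect. The simulation at 204 per arm showed no difference.
- **A reader might infer that the trial is underpowered.** Under the steepening slopes in the table, common-slope power stays between 0.896 and 0.913.

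**Conclusion.** The point holds as a conditional one about efficiency. If the baseline slope steepens by Week 6, the common-slope model under-adjusts the primary contrast. Under the assumptions in the working, the Week 6 variance is about 1% to 12% higher than it need be, which is about 0.3 to 3 power points, and roughly a quarter to just over half of any chance baseline difference stays in the estimate. If the slope is constant, there is no loss. Planned power and type I error are essentially unaffected, the 204 per arm stands, and no average bias is claimed. The recommendation rests on the asymmetry: by-visit adjustment gains when slopes steepen and loses nothing measurable when they do not. This is a minor improvement, and the trial is interpretable without it.

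**What to change.** In 8.4.2 and in the synopsis, add the interaction of Baseline PANSS total score with visit to the fixed effects of the primary MMRM. In 8.4.3, state that the CGI-S model carries the corresponding baseline-by-visit term. Make the SAP match, and settle this before unblinding.

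With six post-baseline visits, the cost is five more fixed-effect parameters per model, against about 612 subjects. No further data are needed, the sample size does not change, and the simulations with constant slopes showed no measurable increase in the standard error.

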8.4.3 Key Secondary Efficacy Analysis

Change from Baseline to Week 6 in the CGI-S scores will be assessed using the same MMRM model used for the change in PANSS scores.

Each study drug dose will be compared with placebo and model-based point estimates for the treatment effects, 95% confidence intervals (CIs), and p-values will be calculated. The analysis set will be the FAS.

In order to control the family-wise Type I error rate, the Hochberg-based matched parallel gatekeeping procedure will be used to account for multiple doses and multiple primary and key secondary endpoints.

The primary and key secondary efficacy hypotheses will be grouped into 2 hierarchical families. Family 1 is the HP-3070-9.0 versus placebo (Hypothesis 1) and HP-3070-18.0 versus placebo (Hypothesis 2), based on the primary endpoint of change from baseline in PANSS total score at Week 6. Family 2 is HP-3070-9.0 versus placebo (Hypothesis 3) and HP3070-18 versus placebo (Hypothesis 4), based on the key secondary endpoint of change from Baseline in CGI-S at Week 6.

Noven Pharmaceuticals, Inc.
HP-3070-GL-04
HP-3070

72

The matched parallel gatekeeping procedure performs multiplicity adjustments as follows:

1. The comparisons for the primary endpoint (Hypotheses 1 and 2) are performed using a truncated Hochberg procedure ($\gamma = 0.9$).
2. The comparisons for CGI-S (Hypotheses 3 and 4) corresponding to the doses that were significant in Step 1 are performed, using a regular Hochberg procedure.

Further details are provided in the SAP.

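### The MMRM fallback list breaks its own ordering rule: full-rank FA0(q) is the unstructured covariance in another form, yet it is placed fourth, after three restrictive structures

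*Protocol*

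**What the plan says.** Section 8.4.2 sets the starting point for the primary MMRM: "An unstructured covariance matrix will be assumed". If that fit does not converge, "the following alternative structures will be attempted in the specified order (from least to most restrictive"). The list opens with "heterogeneous Toeplitz structure (TOEPH), heterogeneous autoregressive (1) (ARH[1]), heterogeneous compound symmetry (CSH"), continues with "No Diagonal Factor Analytic (FA0[q], with q equal to the number of time points"), and ends with TOEP, AR(1) and CS. It adds: "If either ARH(1) or AR(1) structure is used, a random subject intercept will also be included in the model".

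Section 8.4 fixes the meaning of these names by naming the software: "All analyses, summaries, and listings will be performed using SAS". Section 8.4.3 carries the same MMRM over to CGI-S, where "model-based point estimates for the treatment effects, 95% confidence intervals (CIs), and p-values will be calculated". Table 1 schedules the PANSS at six post-baseline visits, Weeks 1 to 6.

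**The concern.** A prespecified fallback list exists so that a convergence failure gives up as little of the planned model as possible, and gives it up in a known order. The protocol says this list does so. But one entry, FA0 at full rank, gives up nothing: it is the planned covariance in a parameterisation that cannot leave the non-negative definite region. Its natural place is first.

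Placed fourth, it is tried only if TOEPH, ARH(1) and CSH have all failed. A single failure of the unstructured fit would therefore replace the intended covariance with a restricted one. That would affect the two PANSS comparisons or, through section 8.4.3, the two CGI-S comparisons, so all four hypotheses in the gatekeeping scheme are exposed. A wrong covariance can distort the Week 6 standard error. When data are missing it also changes how the earlier visits inform the Week 6 estimate.

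**Working it through.** **The plan's own figure.** Section 8.1 gives power of about 0.90 with 204 evaluable subjects per arm, effect size 0.35 (difference 7 and SD 20 in section 8.2.1) and two-sided alpha 0.025. The normal approximation gives 203 per arm for 90% power, and 0.902 power at 204. The noncentral t gives 0.900. The sample size reproduces and this point does not affect it.

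**Step 1: what FA0(q) is.** FA0(q) is V = LL', where L has q columns and zeros above the diagonal. Its parameter count at t time points is q(2t - q + 1)/2. With q = t, L is a full lower triangle and the count is t(t + 1)/2, the same as unstructured. Any covariance matrix has such a factorisation, so FA0(t) and unstructured describe the same set of matrices. Every other structure on the list is a special case of both.

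**Step 2: counts at t = 6, in the protocol's order.**

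| Position | Structure | Parameters |
|---|---|---|
| Start | Unstructured | 6 x 7/2 = 21 |
| 1 | TOEPH | 2 x 6 - 1 = 11 |
| 2 | ARH(1) + random intercept | 7 + 1 = 8 |
| 3 | CSH | 7 |
| 4 | FA0(6) | 6 x (12 - 6 + 1)/2 = 21 |
| 5 | TOEP | 6 |
| 6 | AR(1) + random intercept | 2 + 1 = 3 |
| 7 | CS | 2 |

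The sequence 11, 8, 7, 21, 6, 3, 2 does not fall steadily. Without FA0(6) it does: 11, 8, 7, 6, 3, 2. So FA0 is the only entry out of place. The result does not depend on six visits: t(t + 1)/2 exceeds 2t - 1 for every t of 3 or more (6 against 5 at t = 3).

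**Step 3: numerical check of the equivalence.** FA0(6) was fitted by maximum likelihood to simulated data on 612 subjects. It recovered the unstructured estimate, with a largest element difference of 0.003 and an objective difference of about 1e-9.

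**Step 4: what a restricted structure could do at Week 6.** The protocol states neither a covariance nor a dropout rate, so both are assumed: 204 per arm and monotone dropout, completely at random, of 0%, 25% or 45%. For each assumed true covariance, the large-sample limit of the TOEPH fit was found. Its model-based standard error for the Week 6 difference was then compared with the true standard error of the same estimator. Actual size is 2 x [1 - Phi(2.241 x model SE / true SE)], where 2.241 is the two-sided 0.025 critical value. With no dropout and SD 20 the true SE is 20 x sqrt(2/204) = 1.980.

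| Assumed covariance | TOEPH model SE / true SE, no dropout | Actual size at 0%, 25%, 45% dropout |
|---|---|---|
| SD 10 to 20, adjacent correlation rising 0.70 to 0.93 | 1.728 / 1.980 | 0.050, 0.049, 0.046 |
| SD 10 to 20, adjacent correlation constant 0.85 | 1.980 / 1.980 | 0.025, 0.025, 0.025 |
| SD 10 to 20, adjacent correlation falling 0.93 to 0.70 | 2.371 / 1.980 | 0.007, 0.008, 0.010 |
| Random intercept and slope plus error, SD 9.3 to 19.0 | 1.697 / 1.884 | 0.044, 0.043, 0.040 |
| SD constant 20, adjacent correlation rising 0.70 to 0.93 | 1.728 / 1.980 | 0.050, 0.049, 0.046 |

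In the first row the model SE is 13% too small (1.728/1.980 = 0.873). In the third it is 20% too large (2.371/1.980 = 1.197). In the second, TOEPH happens to be correct and nothing is lost. Over the same settings the size runs from 0.015 to 0.049 for ARH(1) with random intercept and from 0.012 to 0.034 for CSH. Unstructured and FA0(6) give 0.025 throughout.

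**The case against.** **The trigger is uncommon.** With about 612 subjects and six visits the unstructured fit should normally converge, and then nothing changes. Suppose failure occurred in 5% of trials, with TOEPH at its worst size above. The overall size would be 0.95 x 0.025 + 0.05 x 0.050 = 0.026. At 1% it would be 0.99 x 0.025 + 0.01 x 0.050 = 0.025. These failure rates are assumptions. This objection stands and limits the weight of the point.

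**The figures were not computed where the fallback is used.** They rest on well-behaved covariances, under which unstructured would usually fit. A data set that breaks the unstructured fit may be near-singular, and FA0(6) could then end on a boundary. This also stands. The sizes show what is possible and do not forecast what would happen.

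**Perhaps a low-rank FA0 was meant.** FA0(1) has 1 x (12 - 1 + 1)/2 = 6 parameters and would sit acceptably beside TOEP. But the protocol sets q to the number of time points, so that reading is not open.

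**Stronger readings do not hold.** A reader might infer that the fallback makes the standard errors too small and inflates the type I error. The calculations do not support one direction: TOEPH can be anti-conservative, conservative or exact. A reader might also fault the protocol for naming no empirical (sandwich) standard error for restricted structures. Section 8.4 leaves further statistical detail to the SAP, where that choice may properly sit, so it is not part of this point. Nor do the documents show that TOEPH would always converge and leave FA0 unreached. The ordering error does not need that claim.

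**Conclusion.** The ordering error is certain. It follows from the definition of FA0 at full rank and from the protocol's own sentence, and it holds for any number of visits from three up. As written, a failed unstructured fit leads to an 11-parameter structure while a 21-parameter equivalent of the intended model is still untried.

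The consequence is conditional and its direction is unknown. It arises only if unstructured does not converge. The effect on a nominal two-sided 0.025 test then depends on the true covariance, with TOEPH sizes from about 0.007 to 0.050 under the five assumed covariances and 0 to 45% dropout. The planned primary analysis and the sample size are unaffected when unstructured converges. The point is a small correction, worth making because the protocol itself fixes the order: an SAP that follows it inherits the error, and one that departs from it contradicts the protocol.

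**What to change.** In section 8.4.2, move FA0(q), with q equal to the number of time points, to directly after unstructured and before TOEPH. Keep the relative order of the others: TOEPH, ARH(1), CSH, TOEP, AR(1), CS. The parameter counts, including the starting model, then run 21, 21, 11, 8, 7, 6, 3, 2, which agrees with the stated rule. Section 8.4.3 uses the same model, so the corrected order carries over to CGI-S without further text. The SAP should repeat the same order.

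The cost is one sentence and, at most, one extra model fit. It needs no additional subjects and no change to alpha, power or endpoints.
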